9.6 DATA MANAGEMENT

9.6.1 Data Quality Assurance

██████, the contract research organization (CRO), will be responsible for data management of this study, including quality checking of the accuracy, completeness and timeliness of data recorded. Data submitted to the CC manually will be entered into the electronic data capture (EDC) system. CCs will be responsible for data entry into the EDC system. In the event of discrepant data, the CRO will request data clarification

from the CCs, which the CCs will resolve by providing answers to the data queries electronically in the EDC system.

[figure not shown]
The CRO will produce a Data Quality Review Plan that describes the quality checking to be performed on the data.

Roche will perform oversight of the data management of this study, including approval of the CRO data management plans (including Data Quality Review Plan) and guidance.

eCRFs and correction documentation will be maintained in the EDC system audit trail. System backups for data stored at the CRO and records retention for the study data will be consistent with the CRO standard procedures. The CRO will comply with Roche's procedures regarding archiving and record management.

See [Figure 2](#) for data flow overview.

Figure 2 Data Flow Overview

CC = coordinating center; CRO = contract research organization; EDC = electronic data capture; HCP = healthcare provider (e.g., neurologist, obstetrician, infant HCP, midwife)

9.6.2 Electronic Case Report Forms

The CRO will be responsible for designing the eCRFs with input and final approval from the Roche. eCRFs are to be completed using the EDC system. CCs will receive training and have access to a manual for appropriate eCRF completion.

All eCRFs should be completed by designated, trained CC staff. eCRFs should be reviewed and electronically signed and dated by the CC investigator.

At the end of the study, the CC investigator will receive the data related to patients from his or her CC in an electronically readable format (e.g., on a compact disc). Data must be kept with the study records. Acknowledgement of receipt of the data is required.

9.6.3 Source Data Documentation

Roche or designee representatives may conduct onsite source data verification (SDV) visits as defined in the Study Monitoring Plan at the study facilities for the purpose of monitoring various aspects of the study. Roche or designee representatives may confirm that critical protocol data (i.e., source data) entered in the eCRF by authorized CC personnel into the EDC are accurate, complete, and verifiable from source documents (e.g., questionnaires).

Source documents (paper or electronic) are those in which patient data are recorded and documented for the first time.

Before study initiation, the types of source documents that contain study-relevant information will be clearly defined in the Study Monitoring Plan. The Study Monitoring Plan defines which kind of source data – if available from clinical routine – can be used for documentation into an eCRF.

Source documents that are required to verify the validity and completeness of data entered in the eCRF must not be obliterated or destroyed and must be retained per the policy for retention of records described in [Section 9.8.3](#).

To facilitate SDV, the CC investigators must provide direct access to applicable source documents and reports for study-related monitoring, Roche audits, and Institutional Review Board/independent Ethics Committee (IRB/IEC) review. The participating CCs must also allow inspection by applicable health authorities.

9.7 DATA ANALYSIS

Descriptive statistics will be used to summarize the findings; specifically, overall frequency (prevalence, 95% CI) of selected adverse pregnancy outcomes will be calculated, as well as frequencies of specific outcomes, e.g., major congenital malformations (primary outcomes); spontaneous abortions, stillbirths, elective or therapeutic terminations, and preterm births (secondary outcomes). Prevalence and associated 95% CIs will also be calculated for selected adverse fetal, neonatal, and infant outcomes at birth and through at least the first year of life of infants from pregnancies in women with MS exposed to ocrelizumab (i.e., major and minor congenital malformations, small for gestational age, postnatal growth and development, and outcomes related to immune suppression. Similar descriptive analyses summarized above will be performed on the internal comparator group consisting of pregnant women with MS who were not exposed to any MS DMTs (apart from glatiramer acetate). Outcomes will be compared with the internal comparator group and other available

background prevalence from external comparator populations. See Methods of Analysis [Section 9.7.1](#) for additional details.

The comparison to ocrelizumab-exposed women to the internal comparator will be performed using risk ratios (95% CIs) unadjusted and adjusted to relevant covariates, if sufficient number of outcomes are available. See Comparative Analysis [Section 9.7.2](#) for additional details.

All patients enrolled meeting the eligibility criteria will be included in the analytic population. All analyses will be conducted on an overall basis, by earliest trimester of ocrelizumab exposure, as well as presented by enrollment type (i.e., prospective versus retrospective; see [Section 9.2.2](#)). The primary analysis will exclude women who have received first trimester prenatal screening in which either aneuploid disorders or genetic disorders that cause major congenital malformations have been detected. A sensitivity analysis of major congenital malformations will exclude women exposed to any known teratogenic medications during pregnancy. If sufficient numbers are obtained, analyses will also be presented according to maternal age, race/ethnicity, gestational age at enrollment, elective or therapeutic pregnancy termination status, prenatal screening result (positive versus negative), glatiramer acetate exposure (internal comparator group), and other important risk factors. Prevalence and associated 95% CIs will be calculated.

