7.2 STUDY BACKGROUND

Congenital malformations, structural (e.g., cleft lip/palate, heart defects, neural tube defects, heart defects, abnormal limbs) and functional/developmental (e.g., sensory problems, metabolic disorders, nervous system problems, degenerative disorders), affect about 3.0 per 100 live births in the United States (CDC 2008) and are the leading cause of infant deaths (about 20% of all infant deaths) (Matthews et al. 2015). The

European Surveillance of Congenital Anomalies (EUROCAT) estimated the prevalence of congenital anomalies as 23.9 per 1,000 live births from 2003–2007 (Dolk et al. 2010). It is inconclusive whether MS has an impact on risk of adverse pregnancy and infant outcomes. Some studies suggest there is little evidence that MS increases the risk of adverse pregnancy, delivery, or infant outcomes including perinatal mortality, congenital malformations, and delivery complications (Mueller et al. 2002; Dahl et al. 2005; Houtchens 2007). Other studies suggest pregnancies in women with MS are associated with more frequent operative deliveries, decreased infant birth weight or infants small for gestational age compared with women without MS (Dahl et al. 2005; Dahl et al. 2008; Kelly et al. 2009).

Ocrelizumab is a humanized monoclonal antibody of an IgG1 subtype, and immunoglobulins are known to cross the placental barrier. B-cell levels in human neonates following maternal exposure to ocrelizumab have not been studied in clinical studies. There are no adequate and well-controlled data from studies in pregnant women; however transient peripheral B-cell depletion and lymphocytopenia have been reported in infants born to mothers exposed to other anti-CD20 antibodies during pregnancy (Chakravarty et al. 2011; Klink et al. 2008).

It is not known whether ocrelizumab can affect pregnancy outcomes or infant outcomes in humans. However, based on pathophysiological considerations, ocrelizumab might theoretically affect pregnancy outcomes and infant outcomes in the following ways:

- By direct exposure of the fetus to ocrelizumab, which is assumed to occur after the 16th week of gestation as receptor-mediated transplacental transfer of IgG1; this is minimal during the first trimester of pregnancy (Palmeira et al. 2012; Simister 2003)

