9.2.2.1 Ocrelizumab-Exposed

To be eligible to participate in the ocrelizumab-exposed study group, patients must meet the following criteria prior to study entry:

- Patient consent (written or verbal per local regulations or Ethics Committee requirements) obtained prior to enrollment. If the patient is a minor, written consent must be obtained from their parent or legal guardian. Consent will be obtained in compliance with any country-specific regulations or requirements.
- Currently pregnant
- Diagnosed with MS
- Documentation that the patient was exposed to ocrelizumab at any point starting from 6 months prior to LMP
- Agrees to sign the Release of Medical Information Form permitting the study to contact her HCP(s) and the pediatric HCP for medical information
- The outcome of the pregnancy (i.e., pregnancy loss or live birth) must not be known.

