Note: Sample size is calculated using 2-sided exact test at $\alpha=0.05$ significance level. Sample sizes and power calculations are performed using PASS software, version 14. Assumptions: 3% baseline prevalence for major congenital malformations ^a, 15% drop-out rate, 62% live birth rate ^b.

^a CDC 2008

^b FDA 2002; Ventura et al. 2000

Table 3 95% Confidence Intervals for the Prevalence of Adverse Pregnancy Events Based on 153 Pregnancy Outcomes

Approximate Number of Adverse Pregnancy Events (Prevalence of Events) [95% Exact 2-Sided Clopper-Pearson Confidence Interval]		
3% (Major Congenital Malformations) ^a	4% (Major Birth Defects in Ocrelizumab-Exposed Patients) ^b	10% (Preterm Births) ^c
5 (3%) [0.9%, 7.1%]	6 (4%) [1.5%, 8.4%]	15 (10%) [5.7%, 15.9%]
9 (6%) [2.8%, 11.0%]	12 (8%) [4.2%, 13.5%]	31 (20%) [14.0%, 27.2%]
14 (9%) [5.0%, 14.7%]	18 (12%) [7.3%, 18.2%]	46 (30%) [22.9%, 37.9%]

^a CDC 2008

^b Ocrelizumab Investigator's Brochure 2016

^c Ferré et al. 2016

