9.7.1 Methods of Analysis

Demographic information (e.g., age, race/ethnicity, body mass index [BMI]), clinical characteristics, and other potential factors that may affect pregnancy outcome will be described. Descriptive statistics (i.e., mean, SD, median, minimum, and maximum) will be provided for continuous variables. Counts and percentages will be provided for categorical variables. The number of patients with non-missing data will be presented.

Prenatal exposure to ocrelizumab will be summarized based on the timing of exposure by trimester. Total duration of exposure will be calculated using the start date of ocrelizumab use and the stop date +6 months.

The prevalence of spontaneous abortions will be calculated by dividing the number of fetal losses occurring before 20 weeks gestation by the total number of pregnancies. Spontaneous abortions defined as occurring before 22 weeks gestation will also be examined in a sensitivity analysis to account for global variation in the definition for this outcome. Prevalence per 100 pregnancies along with 95% CIs will be presented.

The prevalence of congenital malformations will be calculated using Metropolitan Atlanta Congenital Defects Program (MACDP) and EUROCAT conventions. The total prevalence will be calculated by dividing the number of cases of each event (observed in live births, fetal deaths, elective or therapeutic terminations, and at any gestational age) by the total number of births (stillbirths + live births). The prevalence *at birth* will be

calculated as number of cases observed in live births and stillbirths divided by the total number of births (stillbirths + live births). Prevalence per 100 births along with 95% CIs will be presented.

Prevalence of preterm birth and small for gestational age will be calculated by dividing the number of cases by the total number of births (stillbirths + live births). Prevalence per 100 births and corresponding 95% CIs will be presented.

For growth and developmental delays, the prevalence will be calculated as the number of cases divided by the total number of live births. Prevalence per 100 live births and 95% CIs will be calculated.

Exact 95% CIs including Clopper-Pearson CI for binomial proportion will be assessed.

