Exploratory analyses will be conducted to study the effects of the timing of ocrelizumab exposure before and during pregnancy and cumulative exposure periods on each outcome. Full details on exploratory analyses will be described in the SAP.

The analyses summarized in this Section will also be performed on the internal comparator group consisting of pregnant women with MS who were not exposed to any MS DMTs (apart from glatiramer acetate). The internal comparator group will be analyzed overall (all eligible internal comparator pregnancies) and by two sub-groups: MS DMT-unexposed and glatiramer acetate-exposed.

Full details of the statistical analyses will be provided in the SAP.

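### One exposure window serves every outcome, so women first exposed too late to miscarry count as exposed in the spontaneous abortion rate, and no early-exposure set is named for malformations

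*Protocol*

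**What the plan says.** Section 9.2.2.1 admits a woman to the exposed group on "Documentation that the patient was exposed to ocrelizumab at any point starting from 6 months prior to LMP". Section 9.3.1 records exposure from that point through pregnancy. Neither section sets an upper gestational limit or a window that depends on the outcome.

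Section 9.7 states that "All patients enrolled meeting the eligibility criteria will be included in the analytic population". The one exclusion it gives for the primary analysis concerns aneuploid or genetic disorders found at first-trimester screening. It also requires that "All analyses will be conducted on an overall basis, by earliest trimester of ocrelizumab exposure". That split is not conditional on numbers.

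Section 9.3.2.2.2 defines spontaneous abortion as a loss before 20 weeks. Section 9.7.1 obtains its prevalence by "dividing the number of fetal losses occurring before 20 weeks gestation by the total number of pregnancies", with a sensitivity analysis at 22 weeks. Section 9.7.2 compares malformation, spontaneous abortion and preterm birth rates with the internal and external comparators.

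Section 9.5 sizes the exposed group at 153 outcomes (290 enrolled) for a relative risk of 2.5 against 3%, without reference to when exposure began.

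**The concern.** A woman whose first in-window infusion falls in week n of pregnancy has necessarily reached week n without a loss. If all her time counts as exposed, the weeks before the infusion are event-free by definition. This immortal time comes from the date of exposure, so it remains even if every woman enrols in week 6. It differs from the losses before enrolment that section 9.9 discusses.

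The effect is strongest for spontaneous abortion. First exposure at or after week 20 adds to the denominator and can never add to the numerator. In the split by earliest trimester, the third-trimester stratum is empty of events by definition. The second-trimester stratum holds only survivors of the first trimester and straddles the 20-week limit. DMT-unexposed women in the internal comparator face no such condition, so the risk ratio is pulled down too.

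For major malformations the issue is milder. Women first exposed after the first trimester sit in the overall set and may dilute an effect of early exposure. In a safety registry both errors point towards reassurance.

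**Working it through.** **Inputs from the protocol (section 9.5).** Baseline 3%, relative risk 2.5 (so 7.5%), two-sided alpha 0.05, 80% power, drop-out 15%, live birth rate 62%.

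**Reproducing the plan's figure.** One-sample normal approximation:

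n = [(1.960·√(0.03·0.97) + 0.842·√(0.075·0.925)) / 0.045]² = 152.7, so 153.

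Enrolment: 153 / (0.85·0.62) = 290.3; the protocol states 290. Both figures reproduce. The note to Table 2 says "Sample size is calculated using 2-sided exact test at" the 0.05 level, but 153 is the normal-approximation figure. A two-sided exact test has about 72% power at 153. That is a separate matter, so the method that gives 153 is used below.

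**Malformations: assumptions.** Let f be the share of exposed births first exposed after the first trimester. The documents do not give f, so a range is shown. Assume these women carry the 3% baseline and the others 7.5%.

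- Prevalence p = 0.03·[1 + 1.5·(1 − f)]; apparent relative risk = p / 0.03.
- Power = Φ{[p − 0.03 − 1.960·√(0.03·0.97/n)] / √(p(1 − p)/n)}.
- Example, f = 10%, n = 153: p = 0.0705; (0.0405 − 0.0270) / 0.0207 = 0.65; power 74%.

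| f | p | Apparent RR | Power, all 153 | In-window births | Power, in-window only (RR 2.5) | Enrolment to keep 153 in window |
|---|---|---|---|---|---|---|
| 0 | 7.50% | 2.50 | 80.1% | 153 | 80.1% | 290 (as stated) |
| 5% | 7.27% | 2.43 | 77.3% | 145 | 78.5% | 306 |
| 10% | 7.05% | 2.35 | 74.2% | 138 | 77.0% | 323 |
| 20% | 6.60% | 2.20 | 67.3% | 122 | 73.2% | 363 |

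**Spontaneous abortion, overall rate.** Let g be the share of exposed pregnancies first exposed at or after week 20 (a different share from f, also not given). Observed prevalence = (1 − g) × prevalence among the rest.

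| Assumed prevalence among the rest | g = 5% | g = 10% | g = 20% |
|---|---|---|---|
| 10% | 9.5% | 9.0% | 8.0% |
| 15% | 14.3% | 13.5% | 12.0% |
| 20% | 19.0% | 18.0% | 16.0% |

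This understates the bias, because first exposure between LMP and week 20 also carries some event-free time.

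**Spontaneous abortion, by time of first exposure.** Suppose the drug has no effect and the risk over weeks 6 to 19 is 15% (assumed). The remaining risk is 1 − 0.85^w, where w is the share of the cumulative hazard still to come.

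- Flat weekly hazard: from week 14, w = 6/14, risk 6.7%; from week 18, w = 2/14, risk 2.3%.
- Weekly hazard proportional to exp(−0.2·(week − 6)): the weights sum to 5.18 over weeks 6 to 19, 0.778 from week 14 and 0.165 from week 18. So w = 0.150 and 0.032, risk 2.4% and 0.5%.
- From week 20: zero in either case.

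The exact values depend on the assumed hazard. The direction does not.

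**The case against.** The strongest reply is that the sentence quoted from section 9.7 already separates first exposure by trimester and makes this mandatory. For malformations that largely stands: dilution will be visible, and a reader can look at the early stratum. The protocol also never calls the overall analysis the primary one. What remains is that the sized set has no exposure limit and that no stratum is named to lead. For spontaneous abortion the split is no remedy, because it produces the gradient itself.

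Second, the late-only share is probably small. Such a woman has no infusion from 6 months before LMP to the end of the first trimester and then receives one. Section 7.2 expects exposed pregnancies mainly from contraceptive failure or noncompliance soon after an infusion. This stands and limits the size. Restriction also costs births: at 5% late-only, power is 78.5% restricted against 77.3% diluted, so the gain there is slight. External comparisons rest on point estimates and intervals, so the shift in relative risk matters more than the power.

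Third, a reader might infer more than the documents support:

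- That stillbirth and preterm birth are distorted in the same way. A woman first exposed in mid-pregnancy is still at risk of both, and preterm prevalence is calculated on births, not on all pregnancies.
- That late-exposed women are without malformation risk. Section 7.2 places direct fetal exposure late ("which is assumed to occur after the 16th week of gestation as receptor-mediated transplacental transfer of IgG1"), lists indirect routes and counts functional defects as malformations. Baseline risk is therefore an assumption.
- That the analysis of "cumulative exposure periods on each outcome" is faulty. It is exploratory, its details are left to the SAP, and the protocol does not say that exposure is accumulated to the end of pregnancy.

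**Conclusion.** The point holds for two outcomes. For spontaneous abortion, the definition, the all-pregnancies denominator and the mandatory trimester table together bias the exposed rate downward and build in a protective-looking gradient with an empty third-trimester stratum. The direction is certain from the definitions; the size depends on shares that the protocol does not give. For major malformations the weakness is that no early-exposure set is named for the primary outcome. If late-only women carry baseline risk, the loss is modest at a 5% share (relative risk 2.43, power 77%) and material at 20% (2.20 and 67%). The broad window suits the infant and immune outcomes and should stay for them. This should be corrected, but it does not undermine the registry.

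**What to change.** Amend sections 9.3.1, 9.7 and 9.7.1:

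1. **Spontaneous abortion.** Count a woman as exposed only from her first infusion in the window (from the start of pregnancy if that infusion preceded LMP). Leave first exposure at or after week 20 out of the exposed denominator (week 22 in the sensitivity analysis). Drop the third-trimester stratum for this outcome.
2. **Major malformations.** Make the headline analysis exposure from 6 months before LMP to the end of the first trimester. Show later-only exposure separately and keep the all-exposed result as supportive.
3. **Stillbirth, preterm birth, infant and immune outcomes.** Keep the broad window.

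The cost is wording and programming; section 9.3.1 already records administration dates by trimester. A few late-only women leave the headline malformation set. If 153 in-window outcomes are to be kept, enrolment would be 306 at a 5% late-only share and 323 at 10%; otherwise the slightly lower power should be stated.

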9.7.1 Methods of Analysis

Demographic information (e.g., age, race/ethnicity, body mass index [BMI]), clinical characteristics, and other potential factors that may affect pregnancy outcome will be described. Descriptive statistics (i.e., mean, SD, median, minimum, and maximum) will be provided for continuous variables. Counts and percentages will be provided for categorical variables. The number of patients with non-missing data will be presented.

Prenatal exposure to ocrelizumab will be summarized based on the timing of exposure by trimester. Total duration of exposure will be calculated using the start date of ocrelizumab use and the stop date +6 months.

The prevalence of spontaneous abortions will be calculated by dividing the number of fetal losses occurring before 20 weeks gestation by the total number of pregnancies. Spontaneous abortions defined as occurring before 22 weeks gestation will also be examined in a sensitivity analysis to account for global variation in the definition for this outcome. Prevalence per 100 pregnancies along with 95% CIs will be presented.

The prevalence of congenital malformations will be calculated using Metropolitan Atlanta Congenital Defects Program (MACDP) and EUROCAT conventions. The total prevalence will be calculated by dividing the number of cases of each event (observed in live births, fetal deaths, elective or therapeutic terminations, and at any gestational age) by the total number of births (stillbirths + live births). The prevalence *at birth* will be

calculated as number of cases observed in live births and stillbirths divided by the total number of births (stillbirths + live births). Prevalence per 100 births along with 95% CIs will be presented.

Prevalence of preterm birth and small for gestational age will be calculated by dividing the number of cases by the total number of births (stillbirths + live births). Prevalence per 100 births and corresponding 95% CIs will be presented.

For growth and developmental delays, the prevalence will be calculated as the number of cases divided by the total number of live births. Prevalence per 100 live births and 95% CIs will be calculated.

Exact 95% CIs including Clopper-Pearson CI for binomial proportion will be assessed.

Exploratory analyses will be conducted to study the effects of the timing of ocrelizumab exposure before and during pregnancy and cumulative exposure periods on each outcome. Full details on exploratory analyses will be described in the SAP.

The analyses summarized in this Section will also be performed on the internal comparator group consisting of pregnant women with MS who were not exposed to any MS DMTs (apart from glatiramer acetate). The internal comparator group will be analyzed overall (all eligible internal comparator pregnancies) and by two sub-groups: MS DMT-unexposed and glatiramer acetate-exposed.

Full details of the statistical analyses will be provided in the SAP.

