9.2.2 Study Population

Pregnant patients may be enrolled prospectively from the postmarketing setting or other clinical or observational studies of ocrelizumab. In order to reduce bias that may occur if outcome information is known prior to enrollment, women should be enrolled in the study as soon as their pregnancy is known, preferably in the first trimester.

Women who have had prenatal testing prior to enrollment that could determine the status of the fetus (e.g., amniocentesis, genetic testing, nuchal translucency screen, chorionic villus sampling, and late term ultrasound) will still be considered prospective cases. However, the primary data analysis will exclude women who have received first trimester prenatal screening, in which either aneuploid disorders or genetic disorders that cause major congenital malformations have been detected. Retrospective cases are women where the pregnancy outcome is known, prior to enrollment in the registry, either positive or negative, for major congenital malformations that are unrelated to

genetic or aneuploid disorders. Retrospective cases will be analyzed separately for both primary and secondary analysis.

No exclusion criteria will apply for this study.

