9.3.2.2.2 Spontaneous Abortions

A spontaneous abortion is defined as loss of a fetus due to natural causes at <20 weeks of gestation. If available, information from gross or pathologic examination of the abortus or fetus will be evaluated for structural and chromosomal defects.

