9.9 LIMITATIONS OF THE RESEARCH METHOD

Although all possible measures will be taken to ensure the quality and robustness of the data, there are several limitations inherent to the study design that should be acknowledged.

Spontaneous abortions most frequently occur in early pregnancy, likely before the pregnancy is recognized. Even if the pregnancy is recognized and confirmed, it is

possible that the pregnancy may not be reported to the study if the loss occurred before enrollment into the study. Not capturing all early pregnancy losses will likely lead to an underestimation of the true early pregnancy loss rate. There is no reason to believe that this study will be differentially impacted by this bias so even though the spontaneous early losses may be underestimated, the relative rate compared with the other registries should not be affected.

Reporting outcomes in this study is voluntary and it is possible that not all patients will complete all of the follow-up assessments. If data from a patient and their HCPs is unattainable, the patient will be considered lost to follow-up. It is possible that the outcomes from pregnancies lost to follow-up could differ from those with documented outcomes. Comparisons of the characteristics of patients with completed information and those lost to follow-up will be conducted in an attempt to address this potential bias.

This study plans to enroll both retrospective patients (women where the pregnancy outcome is known, prior to enrollment in the registry, either positive or negative, for major congenital malformations that are unrelated to genetic or aneuploid disorders), and prospective patients (women where the pregnancy outcome is unknown prior to enrollment in the registry, or pre-enrollment prenatal screening for congenital malformations that are unrelated to genetic or aneuploid disorders was not performed). Patients who have been informed about a potential adverse pregnancy outcome prior to enrollment in the study may differentially recall their exposures during early pregnancy and may also have changed their exposures after learning of the outcome. The differential recall may lead to bias, which we will attempt to address with the stratification of primary and secondary outcomes by retrospective and prospective status.

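### Section 9.7.1 divides losses before 20 weeks by all pregnancies although women may enrol at any week: spontaneous abortion prevalence is biased downward, and comparisons are exposed wherever entry times differ

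*Protocol*

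**What the plan says.** Section 9.3.2.2.2 defines spontaneous abortion as "loss of a fetus due to natural causes at <20 weeks of gestation". Section 9.7.1 obtains its prevalence by "dividing the number of fetal losses occurring before 20 weeks gestation by the total number of pregnancies", and adds a sensitivity analysis with a 22-week limit.

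Three provisions determine who is in that denominator:

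- **Entry week.** Section 9.2.2 says that "women should be enrolled in the study as soon as their pregnancy is known, preferably in the first trimester". This is a preference. The same section states "No exclusion criteria will apply for this study", and women already tested by "amniocentesis, genetic testing, nuchal translucency screen, chorionic villus sampling, and late term ultrasound) will still be considered prospective cases".
- **Condition for entry.** Sections 9.2.2.1 and 9.2.2.2 require a current pregnancy, and "The outcome of the pregnancy (i.e., pregnancy loss or live birth) must not be known".
- **Analysis population.** Section 9.7 says "All patients enrolled meeting the eligibility criteria will be included in the analytic population".

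Section 9.7.2 names spontaneous abortion as one of three outcomes to be compared with the internal comparator and with external sources. Section 9.9 accepts that missed early losses will lower the observed rate, but concludes that "the relative rate compared with the other registries should not be affected".

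**The concern.** Spontaneous abortion can occur only before week 20, and its risk is concentrated in early pregnancy, as section 9.9 itself notes. A woman who enrols at week 14 has already passed much of that risk, and one who enrols at week 20 or later has passed all of it. A crude proportion gives both the same weight as a woman observed from week 6. This is left truncation, and the estimator as fixed makes no allowance for it.

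Two things are at stake. The prevalence will be read as a risk of pregnancy loss, which it understates. A comparison of two such proportions also mixes the effect of exposure with any difference in when women came under observation. In a safety registry that could create a signal or hide one.

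**Working it through.** The protocol gives no expected spontaneous abortion rate, no power for it and no distribution of gestational age at entry. There is no planned figure to reproduce, and the size of the bias can only be illustrated.

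**Step 1: what follows without assumptions.** If a share *s* of the denominator enrols at or after week 20, those women alone multiply the prevalence by (1 - *s*): 0.90 for *s* = 10%, 0.75 for *s* = 25%. Losses before enrolment lower it further.

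**Step 2: illustration.** All inputs here are assumptions.

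- Weekly hazard h(w) = c·exp(-d(w - 6)) for w = 6 to 19, with c chosen so that 1 - ∏(1 - h(w)) = 15%. For d = 0.1, 0.2 and 0.3, c = 0.0204, 0.0311 and 0.0422.
- Observable risk of a woman entering in week e: R(e) = 1 - ∏ over w = e to 19 of (1 - h(w)), with R(e) = 0 for e ≥ 20.
- Entry week: normal with mean m and SD 4, rounded to whole weeks, limited to weeks 6-36 and weighted by survival to entry.
- Crude prevalence: the average of R(e) over entry weeks.

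| Decay d | m = 8 | m = 10 | m = 12 | m = 14 | Ratio, 10 v 12 | Ratio, 10 v 14 |
|---|---|---|---|---|---|---|
| 0.1 | 11.1% | 9.1% | 7.1% | 5.1% | 1.3 | 1.8 |
| 0.2 | 10.0% | 7.7% | 5.5% | 3.6% | 1.4 | 2.1 |
| 0.3 | 9.1% | 6.6% | 4.3% | 2.6% | 1.5 | 2.6 |

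The true risk is 15% in every cell. The ratios (from unrounded values) are therefore produced by entry time alone.

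**Step 3: which part matters more.** The share enrolled at or after week 20 is about 1%, 3% and 8% at m = 10, 12 and 14. Removing those women at m = 14 and d = 0.3 moves 2.6% only to 2.6/(1 - 0.08) = 2.8%. Restricting the denominator is necessary, but most of the bias comes from late entry before week 20.

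**Step 4: equal entry times.** This uses a second illustrative model: losses in weeks 5-19, true risk 10-20%, decay 0.1 or 0.2. A weekly hazard ratio of 1.5 gives a risk ratio of 1.43-1.47 when all women are observed from week 5. It gives 1.45-1.49 when both groups share the same staggered entry pattern. The ratio is nearly preserved if entry times match.

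**Step 5: what delayed entry recovers.** In the second model at 15% true risk, with entry in equal quarters at weeks 6, 8, 10 and 12, the crude figure is 7.3-9.2% and the delayed-entry estimate 12.3-13.3%. With entry at weeks 8, 12, 16 and 24 the figures are 3.1-4.5% and 8.2-10.3%. The delayed-entry figure is the correct risk from the earliest entry week (6 or 8) to week 20. Losses before that week cannot be recovered.

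**The case against.** The strongest reply is that the internal comparison is protected. Sections 9.1 and 9.7.2.1 recruit comparators from the same sites with identical follow-up, and section 9.2 applies the same referral model. Section 9.7.2 leaves causal models using baseline characteristics to the SAP, and gestational age is recorded at baseline. Section 9.7 also offers results by gestational age at enrolment if numbers allow. This stands in part. None of it guarantees equal entry times or names delayed entry, but a reader who infers that the internal risk ratio *is* biased goes beyond the documents. They give no entry distribution for either group, and step 4 shows that equal entry nearly preserves the ratio.

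Three other stronger readings also fail:

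- A reader might infer that the words for fetal losses in section 9.7.1 bring induced terminations into the numerator. They do not. Section 9.3.2.2.2 limits the outcome to natural causes, and section 9.3.2.2.1 makes termination a separate outcome.
- A reader might take section 9.9 as a general claim about relative rates. It speaks only of other registries and says nothing about the internal comparator.
- A reader might treat the ratios as forecasts. They depend on an assumed gap in entry time and on the assumed hazard slope.

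It is also true that the outcome is secondary and unpowered, and that the synopsis disclaims inferential testing against external sources. That lowers the severity. It does not repair the estimator, because the protocol itself fixes the denominator rather than leaving it to the SAP.

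**Conclusion.** The point holds as a should-fix. Downward bias in the prevalence follows from the eligibility rules and the fixed denominator. Section 9.9 admits the missed early losses but not the women who are no longer at risk. How many women will enrol at or after week 20 is not stated; the rules only permit it.

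Bias in comparisons is conditional. It is likely against external sources that ascertain pregnancies differently, such as the study in section 9.7.2.2.3, which uses existing claims and population-registry data rather than voluntary enrolment during pregnancy. For the internal comparator it is possible but not shown. With no true effect, a two-week difference in mean entry (week 10 v 12) gives a ratio of 1.3-1.5 and a four-week difference (week 10 v 14) gives 1.8-2.6. Both rest on the assumed 15% risk, entry SD of 4 weeks and hazard decay of 0.1-0.3 per week. The primary malformation analysis is not touched by this point.

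**What to change.** In section 9.7.1:

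- Restrict the spontaneous abortion analysis to women enrolled before 20 weeks (before 22 weeks for the sensitivity analysis).
- Estimate cumulative risk on the gestational-age scale with delayed entry at enrolment, treating elective or therapeutic termination as a competing event. State the gestational week from which the risk is counted.
- Keep the crude proportion as a descriptive figure.

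In section 9.7.2, use the same left-truncated approach for the internal comparison, starting both groups from the same gestational week, and report gestational age at entry by group.

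In section 9.9, qualify the statement on relative rates: it holds only if entry and ascertainment times are similar in the sources compared. Add that losses before the earliest entry week remain unidentifiable under any analysis.

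The cost is protocol and SAP wording, a little more analysis and a slightly wider interval. No new data are needed: the last menstrual period and outcome date are already collected, and enrolment is a recorded contact. The change will not by itself align published external rates, so those comparisons still need the qualification in section 9.9.
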